1. INTRODUCTION

1.1 MEDICAL BACKGROUND

Multiple Myeloma (MM) is a malignant neoplasm of plasma cells that accumulate in bone marrow leading to bone destruction and marrow failure. The age adjusted annual incidence is increasing with approximately 6 new cases per 100,000. The incidence is twice as high in the black US population compared to Caucasians. MM is sensitive to a variety of cytotoxic drugs both as initial treatment or as treatment for relapsed disease. The 5-year survival rate for MM has improved from ~ 25% for newly diagnosed patients in 1975 to ~ 45% in 2006 ([R14-3715](#)). This is mainly attributed to new drugs such as proteasome inhibitors and immunomodulators (IMiDs). However, responses are transient and MM is not considered curable with current approaches. Patients refractory to proteasome inhibitors and IMiDs have a poor prognosis with a median overall survival of 9 months with further treatment and 3 months without ([R14-3714](#)). Outcome is particularly poor in molecularly defined populations such as the high risk subgroup del17p13 positive MM ([R14-3712](#)). New treatment options are therefore urgently required. Although many NBEs are in clinical development for MM no antibody or antibody fragment has yet been registered.

MM patients presenting with active symptomatic disease are initially treated with **primary induction therapy** followed by high dose chemotherapy with autologous stem cell support in selected patients. Patients eligible for intensive treatment are identified by age (with 65 to 75 years constituting the upper limit), lack of comorbidities and preserved renal function. Although this modality has improved survival of younger and fit patients, the median duration of response does not exceed 3 years and few patients remain free of the disease for more than 10 years ([R14-3753](#)). Relapses are due to the failure of high-dose chemotherapy to eradicate residual disease. Consolidation and maintenance approaches have been tested in order to increase the depth and duration of remission. Since maintenance approaches have been hampered by lack of efficacy or tolerability there is still the option of improving survival outcome in the transplant setting by adding novel modalities to induction, consolidation or maintenance regimens. Patients not eligible for high dose therapy usually receive similar induction regimens as the transplant candidates based on the proteasome inhibitor Bortezomib or a Melphalan based combination with Thalidomide. Median OS of Melphalan-Thalidomide-Prednisone (MPT) in elderly patients is 40 months ([P11-05130](#)). Lenalidomide in combination with Dexamethasone is the standard regimen for **relapsed/refractory MM** but may move to the first line setting in transplant ineligible patients based on recent trial results ([R14-15304](#)). Other established strategies in the relapsed setting are repeat induction regimens or bortezomib or IMiD based salvage combinations with alkylating agents. An improvement of outcome (PFS and OS) is clearly needed in the relapsed setting. The patients who have become **refractory** to established treatments and progressed on treatment or within 60 days of completing their last therapy have a dismal prognosis of 9 months OS on treatment and 3 months without ([R14-3714](#)). The unmet need is highest in this population.

Proprietary confidential information.

© 2018 Boehringer Ingelheim International GmbH or one or more of its affiliated companies. All rights reserved.

This document may not - in full or in part - be passed on, reproduced, published or otherwise used without prior written permission.

1.2 DRUG PROFILE

[figure not shown]
B cell maturation antigen (BCMA, TNFRSF17, CD269) is a transmembrane protein belonging to the TNF receptor super family. BCMA expression is selectively induced during late stage plasma cell differentiation and is absent on naïve and memory B cells ([R14-2907](#)). Upon binding to its ligands, B cell activating factor (BAFF) and a proliferation inducing ligand (APRIL), the survival of the bone marrow plasma cells and plasmablasts is promoted ([R14-2906](#)). BCMA does not maintain normal B cell homeostasis but is required for the survival of long lived plasma cells. Studies in BCMA *-/-* mice showed that the survival of long lived bone marrow plasma cells was impaired but B cell development and early humoral immune responses were indistinguishable from wild type mice ([R14-2905](#)). The mRNA expression of BCMA is highly elevated in malignant plasma cell disorders. By contrast, mRNA expression in normal tissues is very low and restricted to lymphoid tissues where normal long lived plasma cells are located. BCMA protein expression is reported to be restricted to plasma cells only. Neither T-cells, myeloid cells ([R14-4494](#)) nor CD34+ hematopoietic stem cells ([R14-2794](#)) express BCMA. The selective expression of BCMA makes it a very attractive target for antibody-based and chimeric antigen receptor (CAR)-based therapies ([R14-2794](#)).

BI 836909 consists of two single chain variable scFv fragments (scFv) that bind to B-cell maturation antigen (BCMA) on tumor cells and CD3 on T-cells. Each of the scFv fragments consists of a VH and VL domain connected with a Glycine/Serine linker. The two scFv fragments are connected with a short Glycine/Serine linker. [REDACTED]

Proprietary confidential information.

© 2018 Boehringer Ingelheim International GmbH or one or more of its affiliated companies. All rights reserved.

[figure not shown]
This document may not - in full or in part - be passed on, reproduced, published or otherwise used without prior written permission.

Proprietary confidential information.

© 2018 Boehringer Ingelheim International GmbH or one or more of its affiliated companies. All rights reserved.

This document may not - in full or in part - be passed on, reproduced, published or otherwise used without prior written permission.

Proprietary confidential information.

© 2018 Boehringer Ingelheim International GmbH or one or more of its affiliated companies. All rights reserved.

2. RATIONALE, OBJECTIVES, AND BENEFIT - RISK ASSESSMENT

2.1 RATIONALE FOR PERFORMING THE TRIAL

Several publications demonstrate that BCMA is universally expressed on the cell surface of MM cells ([R14-2906](#), [R14-3798](#), [R14-3711](#)). A recently published prevalence study showed that 12/67 MM patients had high, 52/67 patients had intermediate and only 3/67 MM patients had low to negative BCMA surface expression. There was no correlation between BCMA expression and disease stage, response to last treatment and time from diagnosis, but, there was a trend towards higher BCMA expression levels in tumors with adverse genetics ([R14-3711](#)). Expression of BCMA is restricted to plasmablasts and long lived plasma cells and is absent on normal human tissues ([R14-2794](#), [R14-2906](#)). Pretesting for BCMA expression is not a requirement for myeloma patients to be entered into the trial.

BI 836909 is an Anti-BCMA Bi-Specific T-cell Engager (BiTE) which binds to BCMA on MM cells as well as CD3 ϵ on T-cells. It is a bispecific new biological entity (NBE) and functions as a bridge between MM cells and cytotoxic T lymphocytes (CTLs) and directs the cytolytic activity of CTLs to MM cells. The BiTE concept has successfully been tested for the CD19xCD3 BiTE blinatumomab which is in late stage clinical development at this time ([R14-3640](#)).

BI 836909 has not yet been tested in humans.

2.2 TRIAL OBJECTIVES

The primary objective of this trial is to determine the maximum tolerated dose (MTD) of BI 836909 administered by continuous i.v. infusion in patients with relapsed and/or refractory multiple myeloma. If the MTD is not reached based on safety findings, a recommended dose for further development will be determined. This will depend on the safety data, pharmacokinetic/pharmacodynamics data and potentially preliminary efficacy data. Secondary objectives are to document the safety and tolerability of BI 836909, to perform pharmacokinetic and pharmacodynamic analyses and to evaluate relevant biological effects in terms of parameters of efficacy. The starting dose is based on a Pharmacologically Active Dose (PAD) estimated from the EC50 of the most sensitive in vitro cytotoxicity assay and pharmacokinetic modelling. Assuming an average body surface area (BSA) of 1.7 m² the proposed starting dose of 0.12 $\mu\text{g}/\text{m}^2/\text{day}$ translates into a starting dose of 0.20 $\mu\text{g}/\text{d}$ given by continuous intravenous injection. In the clinical trial the administered doses will not be BSA-adapted. The proposed starting dose is 4500 fold lower than the HNSTD (540 $\mu\text{g}/\text{m}^2/\text{day}$) and 1500 fold lower than the dose (180 $\mu\text{g}/\text{m}^2/\text{day}$) that did not result in cytokine release in the 4-week toxicology study in cynomolgus monkeys.

2.3 BENEFIT - RISK ASSESSMENT

Progress in understanding the biological behavior of MM has been achieved and effective treatment regimens have been developed. However, these treatments are not curative and most patients with MM still die of their disease. In particular, patients with relapsed and/or refractory multiple myeloma have a need for new therapeutic options.

Proprietary confidential information.

© 2018 Boehringer Ingelheim International GmbH or one or more of its affiliated companies. All rights reserved.

This document may not - in full or in part - be passed on, reproduced, published or otherwise used without prior written permission.

BI 836909 is a Bi-specific T-cell Engager that binds to BCMA on MM cells and on CD3 ϵ on T-cells and therefore functions as a bridge between cancer cells and CTLs and directs the cytolytic activity to the MM cells.

BI 836909 shows strong binding to human BCMA, and comparable cross reactive binding to cynomolgus BCMA. Cells of a bone marrow aspirate of a MM patient containing BCMA positive target cells as well as T autologous cells were incubated for 48 hours with BI 836909. The number of BCMA/CD38 positive cells was determined by flow cytometry over time. The number of viable BCMA/CD38 positive cells decreased in the samples incubated with BI 836909. The cell number in the untreated samples was not reduced.

At time of protocol preparation, BI 836909 has not previously been tested in humans. BCMA is not expressed on other cells than plasma cells. The anticipated side effect profile of BI 836909 based on preclinical studies comprise predominantly depletion of plasma cells and alterations of lymphatic tissues. Changes in WBC (decreases of lymphocytes and monocytes, increases of neutrophils) may occur. Lymphocytopenia may predispose to infections. Given the mode of action cytokine release syndromes may happen. Cytokine release can be associated with clinical symptoms such as fever, chills, nausea, vomiting, hypotension, dyspnoea, tachypnea, headache, tachycardia, rash, and/or hypoxia. CNS toxicities were observed with blinatumomab, the CD19xCD3 BiTE molecule. Whether this side effect is restricted to the CD19 target is still unclear. Considering the experience with other monoclonal antibodies in different indications, infusion-related reactions as well as cytokine release syndrome may occur and have to be differentiated from tumour lysis syndrome. Adverse events like these are frequently reported in patients with malignant diseases and may be due to the underlying disease, the treatment or both. Autoimmune phenomena in terms of anti-drug antibodies may occur. Prophylactic measures will be implemented in this protocol for primary prevention, supportive treatments are available (see [Sections 4.1.4.1](#) and [4.2.1.2](#)).

Current therapy for MM often cause remissions, but nearly all patients eventually relapse and die. There is substantial evidence of an immune-mediated elimination of myeloma cells in the setting of allogeneic hematopoietic stem cell transplantation. There is clearly a great need for new immunotherapies for multiple myeloma and targeting BCMA on MM cells and directing the cytolytic activity of CTLs to MM cells by a BCMA-BiTE might be a major advance in treating patient with refractory or relapsed MM.

Patients with MM may benefit from treatment with BI 836909 in terms of tumour cell reduction, tumour stabilisation, control of tumour-related symptoms and improved survival as BI 836909 targets an epitope of MM cells which has not previously been targeted. The potential benefit of therapy with BI 836909 is expected to outweigh the treatment-related risks.

Although rare, a potential for drug-induced liver injury is under constant surveillance by sponsors and regulators. Therefore, this trial requires timely detection, evaluation, and follow-up of laboratory alterations in selected liver laboratory parameters to ensure patients' safety, see also [Section 5.2.2](#). Advanced and pretreated MM patients may present with elevated liver enzymes at study entry due to liver involvement or pretreatment with hepatotoxic regimen. Transaminase elevations may also occur during treatment with BI 836909 in the context of infusional reactions or cytokine release syndromes which can be managed by experienced

Proprietary confidential information.

© 2018 Boehringer Ingelheim International GmbH or one or more of its affiliated companies. All rights reserved.

This document may not - in full or in part - be passed on, reproduced, published or otherwise used without prior written permission.

investigators. Therefore the definitions for hepatic injury have been modified to reflect the disease state of MM patients entering the trial. Therefore, this trial requires timely detection, evaluation, and follow-up of laboratory alterations in selected liver laboratory parameters to ensure patients' safety, see also [Section 5.2.2](#).

Proprietary confidential information.

© 2018 Boehringer Ingelheim International GmbH or one or more of its affiliated companies. All rights reserved.

This document may not - in full or in part - be passed on, reproduced, published or otherwise used without prior written permission.

3. DESCRIPTION OF DESIGN AND TRIAL POPULATION

3.1 OVERALL TRIAL DESIGN AND PLAN

The trial is an open-label, non-randomized phase I dose-escalation trial with modified 3+3 design to evaluate the tolerability and safety of BI 836909 given as continuous intravenous infusion as well as to determine the MTD or to establish the recommended dose for further development of BI 836909 administered as continuous intravenous infusion.

MTD is defined as the highest dose of the dose level tested where ≤ 1 patient out of 6 develops dose limiting toxicity. If MTD cannot be determined based on safety findings, a recommended dose for further development will be determined based on pharmacokinetic and pharmacodynamics data.

[figure not shown]

Figure 3.1: 1 Overall study design (In case of ongoing clinical benefit, patients can be followed up to collect data for duration of response. Follow-up visits for responders will be at 3, 6 and 12 months after EOT if a patient did not progress, started a new anti-cancer treatment, died, or withdrew informed consent.)

The study consists of the following phases:

- Screening period (day – 21 to day -1): baseline assessments will be performed as well as in- and exclusion criteria will be evaluated
- Treatment period: Treatment will continue for up to five 6-week cycles or until:
 - Disease progression/start of further anticancer treatment

Proprietary confidential information.

© 2018 Boehringer Ingelheim International GmbH or one or more of its affiliated companies. All rights reserved.

This document may not - in full or in part - be passed on, reproduced, published or otherwise used without prior written permission.

- Non-acceptable toxicity
- Patient decision to withdraw consent
- Investigator's decision

In case of ongoing clinical benefit after five courses additional 5 courses may be given if considered indicated by the investigator.

- End of treatment (EOT): this visit will take place as soon as possible after discontinuation of study medication but no later than 1 week after discontinuation of trial drug
- Follow up visit (FU): follow up visit should be performed 30 days after the EOT (REP visit). Patients will be treated for a maximum of 10 cycles. In case of ongoing clinical benefit, patients can be followed up to collect data for duration of response. Follow-up visits for responders will be at 3, 6 and 12 months after EOT if a patient did not progress, started a new anti-cancer treatment, died, or withdrew informed consent. Last patient out is defined as the REPlast visit completed by the last patient. This will be the end of the trial.

For patients who have entered the trial before the approval of the second revision last visit would be defined as the last follow up visit after the approval date.

For patients who have re-consented after the approval of the fourth revision last visit would be defined as above.

The following dose levels will be tested:

Table 3.1: 1 Dose escalation scheme

| Dose level | Dose µg/d | Patients per cohort | Approximate increment to next dose |
|------------|-----------|---------------------|------------------------------------|
| 1 | 0.2 | 1 | 2x |
| 2 | 0.4 | 1 | 2x |
| 3 | 0.8 | 1 | 2x |
| 4 | 1.6 | 1 | 2x |
| 5 | 3.2 | 3 (+3) | 2x |
| 6 | 6.5 | 3 (+3) | 2x |
| 7 | 13 | 3 (+3) | 2x |
| 8 | 25 | 3 (+3) | 2x |
| 9 | 50 | 3 (+3) | 2x |
| 10 | 100* | 3 (+3) | 2x |
| 11 | 200* | 3 (+3) | 2x |
| 12 | 400* | 3 (+3) | 2x |
| 13 | 800* | 3 (+3) | 2x |

*Intermediate dose cohorts with up to 50% increment versus the previous cohort will be entered if determined by the safety committee, in case that the dose of a cohort exceeds MTD (> 1 patient out of 6 with DLT) and the previous cohort is well tolerated.

For example:

Proprietary confidential information.

© 2018 Boehringer Ingelheim International GmbH or one or more of its affiliated companies. All rights reserved.

This document may not - in full or in part - be passed on, reproduced, published or otherwise used without prior written permission.

- 75µg/day in case a dose of 100µg/day exceeds MTD
- 150µg/day in case a dose of 200µg/day exceeds MTD
- 300µg/day in case a dose of 400µg/day exceeds MTD
- 600µg/day in case a dose of 800µg/day exceeds MTD

The above-mentioned intermediate dose cohorts will follow the 3 (+3) design. The starting dose will be 0.20 µg/day given as a continuous intravenous infusion for 4 weeks.

An every 6-week regimen will be tested (4 weeks of continuous intravenous administration of BI 836909 followed by a 2 weeks off-period).

For the dose levels 0.2 to 1.6 µg/day single patient cohorts are entered since no clinical activity is expected at these doses.

If a patient has been on treatment in one of the above-mentioned dose cohorts for 2 weeks without DLT the first patient of the next higher dose cohort will be entered if agreed on by the safety committee. If a patient has reached DLT, then the safety committee recommends the switch to a 3 + 3 cohort for the dose level at which the DLT occurred. Patients may not proceed to the next higher dose level before completion of 6 patients.

One intra-patient dose escalation is allowed within the single patient dose cohorts if the initial dose is tolerated well and no DLT occurs during 1st cycle. In case of DLT additional patients will be entered into this cohort following a 3+3 design.

For the dose levels ≥ 3.2 µg/day 3-6 patients will be treated per dose level and observed for 4 weeks during the first cycle before decision for dose escalation to the next dose cohort is made.

Per dose level 1 patient will be enrolled and treated for 1 week, then further patients will be enrolled. Patients should be entered sequentially. Additional patients should not start treatment before the previous patient has been treated for 48 hours in order to monitor initial transient toxicities due to cytokine release syndrome.

In the dose escalation part the trial safety committee (for details see [Section 3.1.1](#)) can determine to enter additional and intermediate dose cohorts at any time e.g. if DLTs or other safety events, pharmacodynamics activity or antitumor efficacy occur. The safety committee will also determine to switch from single patient cohorts to a 3+3 design at doses below **3.2µg/d** if DLTs, pharmacodynamic activity or antitumor efficacy occur.

PK/PD data might be taken into account for dose escalation decisions if available.

Patients should be entered sequentially. Treatment initiation of more than 1 new patient per day will not be permitted during the dose escalation phase.

Once the MTD or the recommended dose for better characterization of safety and early evaluation of anti-tumour activity is determined up to 6 additional patients will be treated with MTD or the recommended dose.

Proprietary confidential information.

© 2018 Boehringer Ingelheim International GmbH or one or more of its affiliated companies. All rights reserved.

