3.2 DISCUSSION OF TRIAL DESIGN, INCLUDING THE CHOICE OF CONTROL GROUP(S)

The primary objective of this trial is to determine the MTD. The most important secondary objective is to assess the safety of BI 836909 given as continuous intravenous infusion.

For the first 4 doses up to and including 1.6µg/d dose cohorts single patient cohorts have been chosen since no clinical benefit is expected at these low doses.

For the remaining dose cohorts a standard 3+3 design has been chosen as this is an established standard approach in phase I studies in oncology:

The following dose cohorts will be tested as single patient cohorts: 0.2, 0.4, 0.8 and 1.6 µg/day.

If a patient has been on treatment in one of the above-mentioned dose cohorts for 2 weeks without DLT the first patient of the next higher dose cohort will be entered. In case that a DLT has been observed in the single patient cohorts 5 additional patients will be entered on this actual dose level.

Intra-patient dose escalation is allowed once to the next higher dose within the first 4 above-mentioned dose cohorts up to 1.6µg/d.

In case that no DLTs have been observed during the first cycle within the single patient dose cohorts the patient can be treated at the next higher dose level in subsequent cycles. Only one

Proprietary confidential information.

© 2018 Boehringer Ingelheim International GmbH or one or more of its affiliated companies. All rights reserved.

This document may not - in full or in part - be passed on, reproduced, published or otherwise used without prior written permission.

intra-patient dose escalation step is allowed. This approach of intra-patient dose escalation reduces the number of patients treated at pharmacologically inactive doses to a minimum and increases the likelihood of treatment benefit for patients entered at low dose.

Prior to treatment of a patient at the next higher cohort a safety committee quorum needs to be obtained to oversee the observation period of this dose level to make sure that no additional patients must be entered at that dose level and that a patient can be entered at the next higher dose level. If the safety committee recommends treatment of additional patients at the lower dose level 2 additional patients must be entered at the lower dose level first. The 3 + 3 design will then be followed.

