For the dose levels $\geq 3.2 \mu\text{g/day}$ 3-6 patients (3+3 design) will be treated per dose level and observed for 4 weeks before decision for dose escalation to the next dose cohort is made.

If one patient of the cohort of three patients experiences a dose limiting toxicity (DLT) (for definition see [5.2.1.1](#)) within the first cycle (4 weeks of continuous infusion), three additional patients will be treated at the same dose level according to a standard 3+3 design.

If at least two out of up to six patients at a dose level experience a DLT, the MTD has been exceeded and the dose will be de-escalated until a dose level is reached in which at most one DLT out of six patients is observed ([R01-0028](#)).

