7.4 PRIMARY ENDPOINTS

In order to identify the MTD, the number of patients with DLTs during Cycle 1 at each dose level will be displayed descriptively by dose level with the lowest 4 doses pooled. In addition, the number of patients with DLTs during any treatment course will be analysed.

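### Protocol 3.2 does not say whether the five-patient expansion after a DLT in a single-patient cohort stops at a second DLT, and SAP 7.4 pools those four doses in the table meant to identify the MTD

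*Protocol*

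**What the plan says.** **Protocol, after a DLT at 0.2, 0.4, 0.8 or 1.6 µg/day.**

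- Section 3.1 has the safety committee switch that level to a 3+3 cohort: "In case of DLT additional patients will be entered into this cohort following a 3+3 design". It also gates escalation: "Patients may not proceed to the next higher dose level before completion of 6 patients".
- Section 3.2 gives a number without a condition: "In case that a DLT has been observed in the single patient cohorts 5 additional patients will be entered on this actual dose level".
- Section 3.2 has a further sentence for the case where the safety committee recommends more patients at the lower level: "2 additional patients must be entered at the lower dose level first. The 3 + 3 design will then be followed".
- Section 3.2 ends with the rule for an exceeded dose: "If at least two out of up to six patients at a dose level experience a DLT, the MTD has been exceeded". The dose is then lowered until a level shows at most one DLT in six patients.

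**MTD definition.** Protocol 3.1 defines the MTD as the "highest dose of the dose level tested where ≤ 1 patient out of 6 develops dose limiting toxicity". SAP 5.1 has the same definition.

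**Primary display.** Protocol 7.3.1 shows patients with first-course DLTs at each dose level and mentions no pooling. SAP 7.4 has the same purpose, identifying the MTD, but the counts are "displayed descriptively by dose level with the lowest 4 doses pooled". SAP Table 6.1:1 has a separate label for each of the 13 doses, and its footnote 1 makes combining the first four optional, for selected displays.

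**The concern.** The first patient's DLT already counts as one, so a single further DLT at that level meets the exceeded-dose rule. From then on the two parts of Section 3.2 point in different directions: one has five additional patients entered, the other lowers the dose. In a first-in-human trial, a site or committee member should not have to infer which instruction yields.

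The SAP issue arises in the same situation. The MTD rule counts DLTs within one dose level. A row that adds four levels together gives a numerator and denominator to which the rule cannot be applied. At stake are the clarity of one escalation rule and agreement between SAP and protocol on the primary endpoint.

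**Working it through.** The plan has no figure to reproduce here. It gives counting rules, and Protocol 7.7 says that the sample size of up to 50 does not rest on a power calculation. The documents state no DLT rate, so the true rate p at the affected level is an assumption, shown from 0.1 to 0.5.

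**1. Expansion after a first DLT.** Condition on patient 1 having a DLT, and assume that each DLT is known before the next patient starts.

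- Chance of a DLT in patient 2 or 3: 1 − (1 − p)².
- Chance of a second DLT before patient 6: 1 − (1 − p)⁴.
- Expected patients entered after the second DLT if all five are entered regardless: sum over k = 1 to 5 of p(1 − p)^(k−1)(5 − k), where k is the position of that DLT among the five.
- Expected patients at the level under a 3+3 reading (1 + 2, then 3 more only without a second DLT): 3 + 3(1 − p)². The literal reading of the five-patient sentence gives 6.

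For p = 0.2:

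- 1 − 0.64 = 0.36
- 1 − 0.4096 = 0.59
- 0.2×4 + 0.16×3 + 0.128×2 + 0.1024×1 = 1.64
- 3 + 3×0.64 = 4.92

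| p | DLT in patient 2 or 3 | Second DLT before patient 6 | Expected entered after second DLT, literal five | Expected at level, 3+3 reading |
|---|---|---|---|---|
| 0.1 | 0.19 | 0.34 | 0.9 | 5.43 |
| 0.2 | 0.36 | 0.59 | 1.6 | 4.92 |
| 0.3 | 0.51 | 0.76 | 2.2 | 4.47 |
| 0.4 | 0.64 | 0.87 | 2.7 | 4.08 |
| 0.5 | 0.75 | 0.94 | 3.1 | 3.75 |

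The maximum entered after the second DLT is 4, when patient 2 has it and patients 3 to 6 follow.

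**2. What the pooled row can show.** Write each level as DLTs/patients in the order 0.2, 0.4, 0.8, 1.6 µg/day.

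- *Fewer than two DLTs in total.* An exceeded level needs two, so none of the four is exceeded. For example, 0/4 (four times 0/1) and 1/9 (1/6 and three times 0/1) both mean that all four levels were passed.
- *Two DLTs, pooled 2/14.* This fits 0/1, 0/1, 0/6, 2/6: 1.6 is exceeded and the MTD is 0.8. It also fits 1/6, 1/6, 0/1, 0/1: nothing is exceeded. Both add to 14 patients. A pooled 3/19 is ambiguous in the same way.
- *Do the higher rows settle it?* Often, because if 1.6 is exceeded on the way up, no one reaches 3.2. They do not always. Suppose 3.2 µg/day shows 2/3 and the dose is lowered. If 1.6 then fills to 2/6 and 0.8 to 0/6, with 0/1 at 0.2 and 0.4, the pooled row is 2/14 and the MTD is 0.8. If instead 0.4 had passed earlier with 1/6 and 1.6 now fills to 1/6, with 0/1 at 0.2 and 0.8, the pooled row is again 2/14 but the MTD is 1.6. The whole SAP 7.4 table is identical in the two cases.

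With separate columns, each of these outcomes gives one MTD.

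**The case against.** The best defence reads Section 3.2 as a whole: five additional patients is the ceiling and the two-DLT rule is the stop. That rule speaks of a dose level without a lower limit and of up to six patients, which foresees stopping early. This may well be what was meant, but the five-patient sentence carries no condition and nothing calls it a maximum. If the two-DLT rule is instead taken to cover only the levels from 3.2 µg/day discussed just before it, the expansion has no stated stop at all.

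Several other points stand and limit the finding:

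- **Controls.** The safety committee reviews ongoing data and decides the dose-finding steps (Protocol 3.1.1). Entry is sequential, and each enrolment needs the sponsor's written confirmation of dose and date (4.1.4). A reader might infer that patient protection fails. The documents do not support that; the gap is in the written rule.
- **The six-patient gate.** A reader might take "Patients may not proceed to the next higher dose level before completion of 6 patients" as an order to enrol six. It only forbids going up before six, which is compatible with a 3+3 that stops at a second DLT.
- **The two-patient sentence.** A reader might count "2 additional patients must be entered at the lower dose level first" as another conflicting rule. Its trigger is a committee recommendation to add patients, which need not follow a DLT.
- **Other displays.** SAP 7.8 and 7.8.1 also tabulate course 1 DLTs, and SAP 6.1 tabulates by dose group. Nothing requires pooling there, although footnote 1 would permit it. The committee does not depend on the SAP 7.4 table for its decisions.
- **Likelihood.** No clinical activity is expected at these doses (Protocol 3.1), and the description of amendment 2 (28 December 2016) says that no DLT had occurred by then. It does not name the level reached, but the branch had probably not been triggered.

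**Conclusion.** Both points hold in limited form. First, the unconditional five-patient expansion conflicts on its wording with the 3+3 wording and the two-DLT rule. Taken literally it allows up to 4 patients, and on average 0.9 to 3.1 for p from 0.1 to 0.5, to be entered after a second DLT. These figures are conditional on a first DLT, rest on assumed rates and prompt knowledge of each DLT, and leave aside the committee and sponsor controls. They are not an unconditional risk.

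Second, SAP 7.4 departs from Protocol 7.3.1 on the primary display. The pooled row can fail to identify the MTD only when two or more DLTs fall at 0.2 to 1.6 µg/day. Levels from 3.2 µg/day stay separate, and with no DLT at the low levels the pooled and separate tables lead to the same reading. A reader might conclude that the MTD cannot be read at all, which the documents do not support. Practical urgency is low, but the conflicting text is still in protocol version 5.0.

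**What to change.** **SAP 7.4.** For the cycle 1 DLT table, delete the clause that pools the four lowest doses. Show the number of patients with a DLT and the denominator for each dose level on the MTD evaluation set. Optional pooling under footnote 1 of Table 6.1:1 can stay for other displays. Cost: three more columns in one table.

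**Protocol 3.1 and 3.2.** Reconcile the statements on cohort size after a DLT in a single-patient cohort with the two-DLT rule, so that one sequence applies and the text says what happens to the expansion at a second DLT. The sponsor and safety committee decide which sequence. Cost: minor wording in two sections.
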